Based upon preliminary results from the ongoing Phase 1 clinical study AVXS-101-CL-101, at least 80% of treated symptomatic patients with bi-allelic *SMN1* deletions and 2 copies of *SMN2* without the *SMN2* gene modifier mutation (c.859G>C) are expected to achieve the co-primary efficacy endpoint of survival through 14 months of age. It is anticipated that 75% of patients in the PNCR [5] population would not survive beyond 13.6 months of age, and that these control patients will represent a 25% survival rate based upon the natural history of the disease. With this efficacy, an enrolled sample size of 15 patients that meet ITT criteria (assuming 30% of patients are excluded from the analysis) would provide power of >80% to detect a significant difference with $\alpha = 0.05$ using a two sample 2-sided Fisher's exact test, comparing to patient-level data drawn from a published natural history observational study dataset with patients who meet the eligibility criteria for this study (bi-allelic *SMN1* deletions, 2 copies of *SMN2*, age of onset ≤ 6 months of age). The natural history observational study dataset was collected by PNCR network from the study performed at three large, tertiary care centers in the United States (Harvard University, Columbia University, Children's Hospital of Philadelphia; PNCR).

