5.2. Intent-to-Treat (ITT) Population

The ITT population will consist of symptomatic patients with bi-allelic deletion of *SMN1* (exon 7/8 common homozygous deletions) and 2 copies of *SMN2* without the known gene modifier mutation (c.859G>C) who receive an IV infusion of AVXS-101 at less than 180 days of age. The first three patients enrolled must meet the criteria for the Intent-to-Treat Population.

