5.5. PNCR Control Population

The PNCR Natural History dataset ([Finkel, 2014](#)) is drawn from a large natural history study performed on a large cohort of 337 patients with any form of spinal muscular atrophy followed at 3 large, internationally recognized tertiary medical centers with significant expertise in the management of SMA (Harvard University/Boston Children's Hospital, Columbia University and the University of Pennsylvania/Children's Hospital of Philadelphia). Previously identified patients followed in PNCR site clinics and newly diagnosed patients were enrolled. All eligible patients were offered participation in the PNCR study. Study visits were scheduled at baseline and at 2, 4, 6, 9, and 12 months and every 6 months thereafter. The SMA standard of care guidelines published in 2007 were used as a basis for providing uniform care among the study sites. For purposes of this study, sitting (for SMA Type 2) was defined as being able to sit independently for >10 seconds;

children who were unable at any point to achieve this milestone were classified as SMA Type 1.

A natural history control population is drawn from the PNCR Natural History Dataset ([Finkel, 2014](#)) consisting of all patients with age of onset \leq 6 months, bi-allelic deletion of *SMN1* (exon 7/8 common homozygous deletion) and 2 copies of *SMN2* for whom enrollment data (retrospective and prospective) is available to determine survival based on the defined criteria. The *SMN2* modifier mutation (c.859G>C) described by Prior and colleagues (Prior, Thomas W., et. al. "A positive modifier of spinal muscular atrophy in the *SMN2* gene." *The American Journal of Human Genetics* 85.3 (2009): 408-413.) was not assessed in the PNCR study cohort. Based on these criteria, 23 patients from the PNCR dataset are included in the control population. Among them, 17 patients reached the combined endpoint of death or the need for a minimum of 16 hours/day of noninvasive ventilation support for a minimum of 14 continuous days by 13.6 month of age. The survival rate at 13.6 months of age is approximately 25% (17/23), of which the control cohort will be used as comparator with ITT population for survival analysis.

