Due to the difficulty in clinical operation, some landmark visits criteria, like 14 or 18 months of age visits, may not be attained in the protocol defined visit windows. As long as a formal landmark visit cannot be scheduled and the next planned visit is made, for example age of 15 months visit, or survival status is confirmed, for example still survived after age of 18 months, data collected at the unscheduled visit may still be able to map to the landmark visit and included in the corresponding landmark analysis. And protocol deviation will be filed accordingly.

Safety data, such as laboratory results, vital signs, ECGs, and physical exams will be assessed by date and study day. For change from baseline analyses the value associated with the scheduled visit will be used. For summaries of shifts from baseline and potentially significant values all values will be considered for these analyses. Baseline for safety measures will be defined as the latest value before Day 1.

The efficacy data of this study will be compared to the data from the PNCR network. The analysis visit of PNCR will be based on the Visit Month defined in the PNCR dataset.

Table 5: Analysis Time Windows for Dataset from PNCR Network

Scheduled Visit	PNCR
Baseline	≤ Enrollment Date
Month 2	Visit Month 2
Month 4	Visit Month 4
Month 6	Visit Month 6
Month 9	Visit Month 9
Month 12	Visit Month 12
Month 18	Visit Month 18

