Time to death or permanent ventilation through 14 months of age is an additional sensitivity analysis. In case if there is at least 1 patient who is event-free, but discontinue study prior to his/her 14 month birthday, a sensitivity analysis, based on the approach for time to event, will be carried out. In this analysis, time to event will be censored at 14 months of age or at the date of discontinuation. The survival rate at 14 months of age will be estimated by Kaplan-Meier method, and survival curves for AVXS treated patients and the PNCR cohort will be compared using log-rank test at significance level of 0.05.

Additionally, the proportion of patients who experience each of the following events by 14 months of age will be summarized:

- Death
- Permanent ventilation

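### The survival comparison sets no entry-age condition for the PNCR controls to match the treated infants' need to be alive at infusion, so early control events count on one side only

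*SAP*

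**What the plan says.** **Treated group.** SAP Section 5.2 defines the ITT population as symptomatic infants with the specified genotype "who receive an IV infusion of AVXS-101 at less than 180 days of age".

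**Control group.** Section 5.5 takes 23 PNCR patients with onset by 6 months, bi-allelic *SMN1* deletion and two *SMN2* copies, "for whom enrollment data (retrospective and prospective) is available to determine survival based on the defined criteria". It adds that PNCR enrolled both previously identified and newly diagnosed patients. Sections 3.11.1 and 8.1.2 speak of matched patients and a matching cohort, but neither gives a matching rule on age or on status at dosing.

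**Analysis.** The second co-primary is a two-sided Fisher's exact test of event-free survival at 14 months. Section 8.1.2 adds a time-to-event sensitivity analysis, in which "survival curves for AVXS treated patients and the PNCR cohort will be compared using log-rank test at significance level of 0.05". It states the censoring rule but no time origin and no delayed entry. The wording calls for it when at least one event-free patient discontinues before 14 months.

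**Control rate.** Section 5.5 says: "The survival rate at 13.6 months of age is approximately 25% (17/23". The hypotheses in Sections 3.7 and 3.11.1, and the SAS variable for both groups in Section 8.1.2, use 14 months, which Section 6.2.3 sets at 420 days.

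**The concern.** An infant who died before infusion cannot be in the ITT population. A control who died or reached permanent ventilation at the same age stays in the denominator of 23 as a failure. The time between birth and infusion is thus free of death by construction in the treated group, but not in the controls. Taken alone, this favours AVXS-101.

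The test is the second co-primary, and under Section 8.4 both secondary endpoints can be tested only if it succeeds. The hierarchy described in Sections 3.11.1 and 8.4 protects against multiplicity. It gives no protection against a comparator that is not comparable at entry. No planned analysis would show a reader how much of the difference comes from early control events.

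**Working it through.** **Inputs**

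- Section 3.7: two-sided Fisher test at 0.05; treated survival 80% ("at least 80% of treated symptomatic patients"); control survival 25%; 15 enrolled with 30% excluded, so 15 × 0.7 = 10.5, that is 10 or 11 analysed.
- Section 5.5: 23 controls, 17 events by 13.6 months, so 23 − 17 = 6 survivors and 6/23 = 26.1%. The printed 17/23 = 73.9% is the event fraction.
- Assumption: k, the number of the 17 control events that fall before a dosing-equivalent age. The SAP does not give it, so a range of 0 to 8 is shown.

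**The plan's own figure.** Power is the sum, over all outcomes (a, b) with Fisher p < 0.05, of Bin(a; n, 0.80) × Bin(b; 23, 0.25). It is 82.4% at n=10, 84.6% at n=11 and 92.9% at n=15. The stated power above 80% is reproduced.

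**Effect on an observed result.** Removing k early events leaves 6 survivors among 23 − k controls.

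| k | Controls | Survival | p for 12/15 | p for 8/10 |
|---|---|---|---|---|
| 0 | 6/23 | 26.1% | 0.0023 | 0.007 |
| 5 | 6/18 | 33.3% | 0.0135 | 0.046 |
| 7 | 6/16 | 37.5% | 0.029 | 0.051 |
| 8 | 6/15 | 40.0% | 0.060 | 0.099 |

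A result of 12/15 stays significant through k=7. A result of 8/10 loses significance at k=7.

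**Effect on the false-positive rate.** Suppose treatment does nothing. Treated infants, having lived past the early period, then survive at rate 6/(23 − k), while the 23 controls survive at 6/23. The rejection rate is the sum, over outcomes with Fisher p < 0.05, of Bin(a; 15, 6/(23 − k)) × Bin(b; 23, 6/23).

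| k | Two-sided error, n=15 | Part favouring AVXS-101 |
|---|---|---|
| 0 | 2.9% | 1.9% |
| 2 | 3.6% | 2.8% |
| 4 | 4.9% | 4.4% |
| 5 | 6.0% | 5.6% |
| 8 | 12.4% | 12.3% |

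The exact test is conservative at k=0. The nominal 5% is passed from k=5.

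**Effect on power.** Fix the controls at 6/(23 − k) and take 80% true treated survival. At n=15 the successes needed are 9 (k=0), 11 (k=5) and 13 (k=8), giving power of 98%, 84% and 40%. At n=11 power is 84% at k=0 and 62% at k=4.

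**Reading age.** With the SAP's 30-day month, 13.6 × 30 = 408 days, against 420 days for 14 months. Control survival cannot rise between the two ages.

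**The case against.** The controls also had to live long enough to be identified, and some entered PNCR as already known patients. That selection can raise control survival and work against AVXS-101. This stands: the net direction cannot be read from the SAP, and a reader who infers a demonstrated bias in favour of treatment goes further than the text allows. Nor does the SAP say that controls are followed from birth; that is an inference from its use of age.

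It is also fair that nothing shows k to be large. Infusion may take place at any age below 180 days, and 8 of 17 events would have to be early before 12/15 lost significance. If reading the controls at 420 days added one event, 12/15 against 5/15 (k=8) would give p=0.025, and 8/10 against 5/16 (k=7) would give p=0.041.

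A reader might take 13.6 against 14 months as part of the same bias. It is not: it concerns when status is read, not when follow-up starts. The SAS code reads both groups at 14 months, and reading only the controls at 13.6 months would be conservative. The two ages still need reconciling.

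A reader might also bring in Section 6.4, where "The analysis visit of PNCR will be based on the Visit Month defined in the PNCR dataset". That mapping does not enter this test, which uses status at an age.

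What the objection does not remove is the missing rule. Two opposing biases of unknown size are a reason to align entry explicitly.

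**Conclusion.** The point holds in a limited form. As written, the second co-primary compares infants conditioned on being alive at infusion with controls who carry no corresponding condition, and no planned analysis corrects for it. The SAP does not establish the sign or size of the net bias.

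The figures describe one direction only and depend wholly on the assumed k. If k is 4 or less, the two-sided error at n=15 stays within 5%, and a 12/15 result is secure (p=0.007 at k=4). From k=5 the nominal level is exceeded. At k=8 a 12/15 result would no longer be significant. If the treatment effect is as large as planned, the conclusion may well survive, but the plan should let a reader see that. The 17/23 fraction is a clerical error and changes no analysis.

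**What to change.** 1. Keep the planned Fisher test.
2. In all cases, not only when a patient discontinues, add an age-scale Kaplan-Meier and log-rank analysis with delayed entry in both groups: treated infants from age at infusion, controls from age at PNCR entry.
3. Report k. As a sensitivity analysis, repeat the Fisher test with controls who were event-free at an age fixed without using trial data, and apply the same event-free condition to treated infants. A landmark for controls only would count an early-dosed infant's early event as a failure while dropping a control with the same event. Setting it at the trial's median dosing age would make it data-dependent and leave guaranteed survival time for infants dosed later.
4. State that both groups are read at 14 months (420 days), and give the control count at that age in place of the 13.6-month figure.
5. In Section 5.5, correct the survival fraction to 6/23 = 26.1%.

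The cost is SAP wording and programming, since Section 3.7 already plans to use patient-level PNCR data. The downside is fewer controls or less control follow-up, and possibly a less favourable control rate. The changes should be fixed before database lock.

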5.6. Pharmacokinetic Set

Not applicable for this SAP.

5.7. Pharmacodynamic Set

Not applicable for this SAP.

5.8. Protocol Deviations

All deviations will be recorded in the [REDACTED] database and will be categorized in accord with AveXis SOPs. As this is a single dose study, protocol deviations will be described; however, there will be no separate statistical analysis.

6. GENERAL ASPECTS FOR STATISTICAL ANALYSIS

6.1. General Methods

All hypothesis testing will be conducted at one-sided with significance level $\alpha=0.025$ or two-sided, at significance level $\alpha=0.05$, as appropriate. Categorical measures, such as percent surviving event-free, will be summarized using count and percentages.

Continuous data, such as CHOP-INTEND scores, will be summarized using count, mean, median, standard deviation (SD), minimum, and maximum. For continuous data specified to be analyzed using parametric procedures, non-parametric procedures will be used if assumptions of parametric tests are not met.

Summary tables, listings, and figures, and statistical analyses will be done using SAS version 9.3 or higher.

Efficacy analyses will be conducted on the ITT and the Efficacy Completers population, as indicated. Additional efficacy analyses for other subgroups of patients may also be conducted, as appropriate. The analysis based on the ITT population will be considered as the primary analysis. Safety analyses will be conducted on the Safety Analysis population only.

6.2. Key Definitions

6.2.1. Definition of Baseline

The baseline value refers to the last non-missing measurement collected before gene therapy infusion of study drug. On Study Day 1, all assessments should be performed prior to administering the gene therapy infusion of study drug per protocol. The baseline value is therefore determined by the last non-missing measurement collected on or before the first day of study drug administration. If multiple measurements are recorded on the same day, the last measurement recorded prior to the gene therapy infusion will be used as the baseline value. If these multiple measurements occur at the same time or time is not available, then the average of these measurements (for continuous data) or the worst among these measurements (for categorical data) will be considered as the baseline value. This same baseline value will be used for the treatment and post-treatment periods. For some special measures, the baseline value will be defined explicitly in the corresponding section.

The baseline values will be the first non-missing values collected for the control patients from the PNCR dataset.

6.2.2. Definition of Study Days (Days Relative to the Gene Therapy Infusion)

Study Days are calculated for each time point in the treatment period relative to the gene therapy infusion of study drug. Study Days are negative values when the time point of interest is prior to the study drug infusion day. Study Days are positive values when the time point of interest is after the first study drug dose day. Study Day 1 is the day of the infusion of the gene therapy study drug.

6.2.3. Definition of Final Treatment Value

For the purposes of the co-primary endpoint of survival (see [Section 8.1.2](#)), the first non-missing value after the participant reaches 14 months of age. There is no upper bound for the “14 months” age visit; that is, no visit is too late to represent the “14 months of age” analysis. The earliest visit on or after 420 days of age will be used in the “14 months of age” analysis.

For all other endpoints, including the co-primary endpoint of functional independent sitting (see [Section 8.1.1](#)), the co-secondary endpoints of “maintain ability to thrive” (see [Section 8.2.1](#)), “independence of ventilatory support” (see [Section 8.2.2](#)), and [REDACTED]

[REDACTED] the final treatment value for each patient is the first non-missing value on or after the participant reaches 18 months of age (540 days) with an upper limit of 570 days. Thus, the earliest visit between 540 and 570 days of age, inclusive, will be used in the “18 months of age” analysis.

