This is a Phase 3, open-label, single-arm, single-dose study of AVXS101 (gene replacement therapy) in patients with SMA Type 1 with 1 or 2 copies of *SMN2*. The study includes 3 study periods: screening, gene replacement therapy, and follow-up (Figure 1). During the screening period (Days -30 to -2), patients undergo screening procedures to determine eligibility for study enrollment. Those who meet the entry criteria will enter the in-patient gene replacement therapy period (Day -1 to Day 3). On Day -1, patients will be admitted to the hospital for pre-treatment baseline procedures. On Day 1, patients will receive a one-time IV infusion of the equivalent of AVXS-101 1.1×10^{14} vg/kg over approximately 30–60 minutes, dependent upon total volume required per patient weight, and will undergo in-patient safety monitoring over the next 48 hours. Patients may be discharged 48 hours after gene replacement therapy, based on investigator judgment. During the outpatient follow-up period (Day 4 to End of Study at 18 months of age), patients will return at regularly scheduled intervals for efficacy and safety assessments until the patient reaches 18 months of age. Any missed visit should be rescheduled as soon as possible, but within 7 days and still within the required visit window.

All post-treatment visits will be relative to the date on which gene replacement therapy is administered, except for the 14 and 18 months of age visits, which will be relative to the patient's date of birth. For the 14 and 18 months of age visits, the patient will return within 0 to 14 days after the date on which the patient reaches 14 and 18 months of age, respectively. The 18 months of age visit will also serve as the End of Study visit. After the End of Study visit, eligible patients may roll over into the long-term follow-up study.

Figure 1: Study Design Schematic

Note: After the End of Study visit at 18 months of age, eligible patients may directly roll over into the long-term follow-up study.

ET = early termination

a All post-treatment visits will be relative to the date on which gene replacement therapy is administered, except for the 14 and 18 months of age visits, which will be relative to the patient's date of birth.

A schedule of study assessments is provided in [Table 1](#). Efficacy will be assessed by primary, secondary, [REDACTED] endpoints (see [Section 4.1, Efficacy Endpoints](#): (see [Section 8 for Details](#)) and [REDACTED]

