6.2.4. Derived and Transformed Data

6.2.4.1. Primary Efficacy Variables

The co-primary efficacy endpoint is functional independent sitting at the 18 months of age visit.

Functional independent sitting: this is assessed by video evaluation by an expert reviewer of videos taken either at scheduled visits (see

Table 4 and

Table 5) or provided by parent/legal guardian, if patient meets the criterion:

- Child sits alone without support for at least 30 seconds. This will be collected from external dataset.

The other co-primary endpoint, event-free survival, is defined as avoidance of any one of the following events up to 14 months of age, whichever occurred first:

- Death, *or*
- Tracheostomy, *or*
- Noninvasive Ventilatory support \geq 16-hour per day *and* continuously \geq 14 days

Usage data for patients using non-invasive ventilatory support will be extracted directly from the device (Triology 100, Trilogy 200) on an SD card, and transferred as an external dataset. Average daily use of non-invasive ventilatory support by visits (if available) will be calculated. If a patient did not have a Trilogy device at baseline and was using non-invasive ventilatory support prior to screening, the average daily usage will be based on parent report and documented in the source documentation. As a secondary analysis, the amount of ventilation support will be categorized into None, >0 - \leq 12 hours, >12 - $<$ 16 hours, \geq 16 or permanent ventilation. The count and percent of patients in each ventilation support category at each visit (if available) will be displayed.

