6.4. Visit Windows

For efficacy analysis, the time windows specified in

Table 4 describe how efficacy data will be assigned to protocol-specified time points, as displayed in the Schedule of Assessments in SAP [Section 3.5.1](#). All time points and corresponding time windows are defined based on Dosing Date.

If more than one efficacy observation for a specific assessment is included in a time window, the assessment closer to the nominal time will be used. If there are two efficacy observations equally distant to the nominal time, the latest one will be used in analyses. Any efficacy assessments occurring outside the analysis windows will be considered an assessment of an unscheduled visit.

Table 4: Analysis Time Windows of Bayley Scales, CHOP-INTEND, Development Milestones and Pulmonary Exam*

Scheduled Visit	Nominal Days (Study Day)	Acceptable Analysis Window in Study Days (Min Day – Max Day)
Baseline	-	<1
Month 1	30	1 to 44
Month 2	60	45 to 74
Month 3	90	75 to 104
Month 4	120	105 to 134
Month 5	150	135 to 164
Month 6	180	165 to 194
Month 7	210	195 to 224
Month 8	240	225 to 254
Month 9	270	255 to 284
Month 10	300	285 to 314
Month 11	330	315 to 344
Month 12	360	345 to 374
Month 13	390	376 to 404

Scheduled Visit	Nominal Days (Study Day)	Acceptable Analysis Window in Study Days (Min Day – Max Day)
Month 14	420	405 to 434
Month 15	450	435 to 464
Month 16	480	465 to 494
Month 17	510	495 to 539
Month 18	540	540 to 570
Final Treatment Visit and 14 Months of Age Analysis Window		0 to ≤14 days after patient reaches 14 months of age (420-434 days of age) visit window; 0 to ≤14 days after patient reaches 18 months of age (540 days of age) visit window

*Depending on age at time of dosing, patients will complete varying number of visits. The patient must complete a visit within 2 weeks after reaching 14 months of age; subsequent visits will be scheduled from that visit date. The patient must also complete the final study visit within 2 weeks after reaching 18 months of age.

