8. EFFICACY

8.1. Primary Efficacy Endpoints and Analysis

8.1.1. Co-Primary Efficacy Endpoint: Functional Independent Sitting at 18 months of age

An independent expert reviewer will evaluate recorded videos of CHOP-INTEND or Bayley Scales assessments conducted at clinic visits. The reviewer will judge whether the video reveals evidence of the milestone achievement of functional independent sitting [REDACTED].

During the Screening visit, the physical therapist will complete an assessment of baseline milestone achievement, including functional independent sitting; this assessment must address all milestones/items noted in [Appendix 21.1](#) that are at or below the child's expected function for age. Items that are below the child's expected function for age that are not successfully achieved during the baseline evaluation should be repeated at subsequent visits until successfully performed.

The milestones of sitting independently (Bayley Scales gross motor subtests item 22 and 26) will be assessed at every subsequent visit regardless of starting point on the scale. These milestones will also be assessed at the 18 months of age visit, regardless of previous attainment, as the Bayley Scales do not necessarily require the child to repeat previously attained milestones.

The number and percent of patients whom, through video evidence, exhibit the milestone achievement of independent sitting for at least 30 seconds at 18 months of age study visit will be summarized for the ITT population. Potential missing values will be imputed per [Section 6.3](#). A one-sided Exact Binomial Test will be used to test the null hypothesis of $p=0.1\%$ at significance level of 0.025. Furthermore, the corresponding 97.5% confidence intervals will be estimated by the exact method for binomial proportions.

In case for the presence of missing value, sensitivity analyses outlined in [Section 6.3](#) will be carried out to evaluate the appropriateness of assumptions for the missing data.

Additionally, for patients who achieve the functional independent sitting at 18 months of age visit, the age at which the subjects first achieved independent sitting for 30 seconds will be summarized.

8.1.2. Co-Primary Efficacy Endpoint: Avoidance of Death or Surrogate for Death (Permanent Ventilation)

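### SAP rules conflict on which visit and which video decide 18-month sitting: Section 6.2.3 caps the age at 570 days, Section 6.4 allows later mapping without a cap

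*SAP*

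**What the plan says.** Five places in the SAP bear on which assessment determines the sitting endpoint.

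- **Section 6.2.3** names sitting and states that "the earliest visit between 540 and 570 days of age, inclusive, will be used in the" 18-month analysis. For survival at 14 months, the same section expressly sets no upper bound, so the cap on sitting looks deliberate.
- **Section 6.4, Table 4.** In the column for acceptable analysis windows, the final-treatment row gives "0 to ≤14 days after patient reaches 18 months of age (540 days of age) visit window", which is 540-554 days of age. The text above the table ties all windows to the dosing date and prefers the assessment nearest the nominal time, or the later one if tied. It adds: "Any efficacy assessments occurring outside the analysis windows will be considered an assessment of an unscheduled visit".
- **Section 6.4, text after Table 4.** Where the 14- or 18-month visit was not achieved in its window, "data collected at the unscheduled visit may still be able to map to the landmark visit and included in the corresponding landmark analysis". No latest age is given.
- **Section 6.2.4.1** defines the primary variable from videos taken at scheduled visits (it refers to Table 4) "or provided by parent/legal guardian, if patient meets the criterion".
- **Section 8.1.1** describes only "recorded videos of CHOP-INTEND or Bayley Scales assessments conducted at clinic visits", and has sitting assessed again at 18 months whether or not it was attained before.

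Section 6.3 imputes missing co-primary values as non-response. No section says which of these rules prevails.

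**The concern.** Sitting is tested first (Section 8.4), the trial is open-label (Section 3.8), and the analysis set is about 15 children. Responder status should follow from one rule fixed before the data are seen. Here a child who comes late can be a failure under Section 6.2.3 and a possible responder under the text after Table 4. Because that text is permissive, someone must decide case by case, when the child's sitting result may already be known. The protocol cannot be relied on to settle the matter, since Section 2 says the SAP supersedes its statistical considerations.

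What is at stake is mainly the reported proportion and its confidence limit.

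**Working it through.** **1. The window rules side by side**

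| First visit at or after day 540 of age | Section 6.2.3 | Table 4, final row | Text after Table 4 |
|---|---|---|---|
| 540-554 | used | in window | not needed |
| 555-570 | used | outside, so unscheduled | may be mapped |
| after 570 | no value; non-response by 6.3 | outside, so unscheduled | may be mapped |

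The last line is the hard contradiction. The middle line conflicts only if the Table 4 row is read as an analysis window. That 6.3 applies in the last line is a short inference: 6.2.3 then yields no value, and 6.3 imputes missing values as failures.

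**2. The clock**

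With the SAP's day conventions, a child dosed at age d days reaches study day s at age s + d - 1, and reaches age 540 on study day 540 - d + 1.

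- d = 120: age 540 is study day 421, inside Table 4's Month 14 row (405-434). Study days 540-570, the Month 18 row, are ages 659-689.
- d = 179: age 540 is study day 362, inside the Month 12 row (345-374). The Month 18 row is ages 718-748.
- The last visit is due by age 540 + 14 = 554. To be at study day 540 by then requires 540 + d - 1 ≤ 554, so d ≤ 15.

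Table 4's Month 18 row carries the same digits as 6.2.3 on a different clock, and almost no child can reach it.

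**3. The selection rule**

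Section 6.2.3 takes the earliest visit; Section 6.4 takes the nearest to nominal, the later if tied. If the nominal point is day 540 of age and the window opens on that day, the nearest visit is also the earliest. The two rules then differ only for assessments on the same day. This is a disagreement in wording with little practical effect once the clock is settled.

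**4. The plan's own power figure**

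Inputs from Section 3.7: null 0.1%, one-sided α = 0.025, true rate 30-40%, 15 children less about 30% (15 × 0.7 = 10.5, so 10 or 11). Stated power is above 90%.

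- One responder rejects: 1 - 0.999^15 = 0.0149; at n=10, 1 - 0.999^10 = 0.0100.
- Power at n=10: 1 - 0.7^10 = 97.2% and 1 - 0.6^10 = 99.4%. At n=11: 98.0% and 99.6%. At n=15: 99.5% and 99.95%.

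The stated figure is reproduced.

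**5. Effect of one reclassified child**

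- Estimate: 1/15 = 6.7 points; 1/10 = 10 points.
- Exact lower 97.5% limit (Beta quantile 0.025 with parameters x and n - x + 1): 5/15 = 33.3%, limit 11.8%; 6/15 = 40.0%, limit 16.3%.
- One child can alter the test decision only between 0 and 1 responders, which requires a count of at most 1. At n=15, P(X ≤ 1) = 0.7^15 + 15 × 0.3 × 0.7^14 = 0.0047 + 0.0305 = 3.5% at a true rate of 30%, and 0.5% at 40%. At n=10 it is 14.9% and 4.6%.

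**The case against.** The best defence is that Section 6.2.3 is the endpoint-specific rule, names sitting, and would naturally prevail. Days 540-554 lie inside 540-570 and match the scheduling window of Section 3.5 ("the patient will return within 0 to 14 days after the date on which the patient reaches 14 and 18 months of age, respectively"); the Table 4 row itself uses the term visit window. An unscheduled label does not by itself exclude a day-560 visit under 6.2.3. The mapping text applies only when the landmark visit could not be scheduled, so it does not reopen a failed assessment made at 540-570 days. It also requires a protocol deviation, which makes its use visible. The 18-month visit ends the study, so few children should be seen later. Finally, only milestones confirmed by the independent reviewer count (Section 4.1.1).

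Much of this stands and narrows the point. It does not remove the contradiction: the SAP never says that 6.2.3 prevails, the mapping text names the 18-month visit and has no limit, and central confirmation governs how a video is read, not which visit or video is eligible.

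Three stronger readings are tempting but not supported:

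- A reader might infer that a child filmed sitting at home at 13 months, but not sitting at 18 months, could be a responder. Section 6.2.4.1 opens by tying the endpoint to the 18-month visit, and Section 8.1.1 requires reassessment then. Home videos have their own role in Section 6.2.4.3, dating first achievement.
- A reader might infer that visits counted in calendar months would fall outside the window. Section 1.2 fixes a month at 30 days and Table 4 prints day 540.
- A reader might infer that the trial's success hangs on one child. That holds only at 0 versus 1 responder, and the one-responder threshold comes from the 0.1% null, not from the windows.

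**Conclusion.** The point holds in a limited form. Section 6.2.3 and the text after Table 4 give different responder status to a child with no visit by day 570, and no precedence is stated. Table 4's final row, clock and selection wording also disagree with 6.2.3, although the 540-554 window can be read as scheduling only. The admissible video source is described in two ways.

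The size is 6.7 percentage points per reclassified child at n=15, with a matching shift in the confidence limit. At the SAP's assumed 30-40% rate the significance decision is unlikely to change. These figures assume 15 analysed children and a single reclassified child; how many children would be seen late cannot be known from the SAP. The 6.2.3 window also serves both co-secondary endpoints, so the window conflict reaches them too.

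**What to change.** Before database lock, amend the SAP wording:

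1. State that Section 6.2.3 prevails for sitting: a centrally confirmed clinic video at the earliest visit at 540-570 days of age, otherwise non-responder. Repeat this rule in 8.1.1.
2. Change Table 4's final row to 540-570 days of age for the 18-month analysis, and exempt it from the dosing-date clock and the nearest-to-nominal rule.
3. In the text after Table 4, bar mapping beyond day 570 from the primary sitting analysis, and show later visits in a sensitivity analysis.
4. In 6.2.4.1, confine home videos to age at first achievement, in line with 6.2.4.3.

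The sample size and stated power calculation are unchanged. The cost is that a child first seen after day 570 becomes a non-responder in the primary analysis. If 10% to 30% of children were lost this way (an assumed range), power at n=10 and a 30% rate would be 1 - 0.73^10 = 95.7% to 1 - 0.79^10 = 90.5%, still above the stated 90%.
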